**Background, Rationale and Context**

When the coronavirus became a pandemic in early 2020, wearing masks became mandatory in all public places. This lead to certain challenges such as difficulty communicating among hearing-impaired individuals who may rely on lip reading, and the use of clear masks has been shown to alleviate this challenge.(Atcherson et al) In the operating room, masks have been worn to reduce the risk of surgical site infections. Surgical masks are currently being worn in the operating room during placement of deep brain stimulators (DBS) in awake patients for the treatment of medically refractory movement disorders, including Parkinson's disease and Essential Tremor. During DBS surgery, a series of questions and assessments are carried out by a neurologist in the operating room to confirm location and appropriate placement of the stimulator, requiring patients to be awake and participatory. As the neurologist traditionally wears a surgical mask that prevents patients from lip reading, a surgical mask without a clear window has the potential to hinder the communication between the neurologist and the patient. It is of vital importance that the patient understands and accurately answers the neurologist's questions to facilitate optimal placement of the DBS electrode while maximizing operative efficiency.

Since the availability of clear masks has increased in the wake of the COVID-19 pandemic, surgeons have found improved satisfaction among patients whose surgeons use clear masks when discussing or explaining surgery in the outpatient setting. (Kratzke et al) One example of a clear mask is The Communicator (Safe'N'Clear, Inc., Davidson, NC, USA), which is the only FDA-approved, ASTM Level 1 surgical mask. It has a 4.75 x 1.35 inch clear window that allows for clear visibility of the mouth.

Clear masks have not been evaluated in the intraoperative setting. Our hypothesis is that the utilization of clear surgical masks in the operating room will lead to improved satisfaction and enhance communication for patients undergoing DBS surgery.

**Objective**

To evaluate patients' experience during awake brain surgery when the communicating neurologist wears a clear face mask compared with a standard surgical mask.

**Methods and Measures**

**Design**

Single-center prospective randomized controlled study

**Setting**

Wake Forest Baptist Medical Center

**Subject selection criteria**

Study participants who meet the below criteria will be approached for potential participation prior to surgery.

- **Inclusion Criteria**
  - Age  $\geq$ 18 years
  - Patients electing to undergo deep brain stimulator placement
  - Patient in whom general anesthesia is not planned for stimulator target localization
- **Exclusion Criteria**
  - Patients who do not give consent
  - Patients who do not undergo DBS placement
  - Patients who are blind or have a severe visual impairment
  - Non-English speaking patients (i.e., patients for whom an interpreter would be needed to conduct the intra-operative assessment)
- **Sample Size**
  - Based on statistical calculations and projections, the target sample size will be 60 patients.

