## **Interventions and Interactions**

Patients who both elect to undergo DBS surgery and agree to participate in this study will have a record created in the study database. All patients scheduled for a DBS phase I surgery will be contacted via telephone in the days prior to their scheduled surgery to discuss the possibility of study participation. This will be done to give the patient time to consider study participation in order to avoid delays the morning of surgery. The morning of surgery the patient will be approached in pre-operative holding room to discuss participation in the study and if amenable sign consent for participation. This discussion will inform the patient that minor changes are being made in an attempt to improve the patient experience, but limited information regarding what steps exactly will be provided so as to reduce potential bias that might result from the patient knowing we are studying a new mask type. If the patient agrees to participation, a consent form will be signed and as a baseline will undergo the Hearing Handicap Inventory for the Elderly (HHIE-S) questionnaire before the operation (Appendix 1). The patient's record in the electronic study database will then be created and randomized to one of two groups. Group A will experience the neurologist wearing a clear mask, and group B will experience the neurologist wearing a standard covered mask. The patient and all other intra-operative personnel will wear a covered surgical mask.

Following standard surgical protocol, the DBS surgery will proceed with the patient awake. First, a stereotactic frame is securely attached to the patient's head and the patient is positioned appropriately. Local anesthetic is used for the neurosurgeon to obtain access through the scalp and skull. A microelectrode is then stereotactically placed using headframe coordinates. The neurosurgeon sets up the motor apparatus to allow the neurologist to advance the microelectrode to the appropriate deep brain target, operating the motor from a non-sterile station arranged next to the patient. The microelectrode will stimulate and record neuronal activity, during which time the neurologist will ask the patient questions to assess for changes in symptoms. These questions typically are of the following nature:

- Do you notice any tingling or pulling of the mouth or face?
- Do you see any flashes of light in your vision?
- Do you feel any tingling or heaviness of an arm or leg?

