- Do you notice any metallic or strange taste?
- Can you draw a spiral on this piece of paper?
- Can you hold your arm out in front of you and keep it still?

During a routine DBS surgery, the neurologist is positioned in view of the patient while operating the electrode motor and asking the above questions. Microelectrode stimulation and recording will conclude

when the appropriate target has been reached; that is, when simulation achieves both symptom improvement without new neurologic symptoms. At that point, the microelectrode is withdrawn and the macroelectrode is placed. The macroelectrode is stimulated in the determined position to again confirm symptom improvement without new neurologic symptom or deficit, and when confirmed the neurosurgeon will secure the macroelectrode in place. At this point, the neurologist's testing portion is complete, and the neurologist exits the operating room while the neurosurgeon completes the implantation.

For patients who agree to study participation, the neurologist will wear the mask type assigned by the randomization group for the duration of involvement in the surgery. At the conclusion of the neurologist's interaction with the patient, the patient will be asked a series of questions (presented in Appendix 2, Data collection form) to evaluate the communication experience. This step will be performed by another member of the study team (not the participating neurologist) who will read from the questionnaire and record the patient's responses using the Likert scale (defined in Appendix 2). During questioning, the neurologist will step out of the operating room to reduce potential bias from the patients answering subjective questions in front of the neurologist.

At the conclusion of the questionnaire, the patient will undergo a short debriefing regarding the aims of the study, specifically the revelation that the purpose of the study is to evaluate the use of a clear surgical mask on the patient's experience, as assessed by the questionnaire.

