## **Outcomes and Statistical Plan**

Data will be gathered based on the attached Data Collection Form (Appendix 2). Answers to the questionnaire will be deidentified.

Power calculations will be performed considering the primary endpoint of a dichotomous response to question #1 of the CG-CAHPS. Thirty subjects per group will be needed to achieve 80% power to detect a difference of 26% or more between proportions (hypothesized standard of care mask positive response rate of 73% versus clear mask positive response rate of 99%) with alpha of 5% using conservative two-sided Fisher's Exact Test. Therefore the enrollment goal will be 60 subjects total.

Secondary outcomes will include differences in response to the remaining quantitative questions of the CG-CAHPS and free text responses to the final question. As the quantitative question responses are on a Likert scale, responses 1-3 will be considered negative and 4 will be considered positive thereby converting the outcome to binary according to the top box method. Fisher's Exact Test will be used to investigate a difference between the standard of care mask and the clear mask for all dichotomous outcomes. P-values < 0.05 will be considered statistically significant. A content analysis will be performed on the free responses to investigate distinct themes.

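### Does excluding patients who do not undergo DBS placement remove randomised patients on a surgical outcome?

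*Combined protocol and SAP*

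**What the plan says.** Under Subject selection criteria, the lead-in reads "Study participants who meet the below criteria will be approached for potential participation prior to surgery". Inclusion requires "Patients electing to undergo deep brain stimulator placement"; among the exclusions is "Patients who do not undergo DBS placement".

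Subject Recruitment Methods (Human Subjects Protection) says that potential participants are screened against the inclusion and exclusion criteria and approached only then, with consent signed before any data collection or randomisation.

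Interventions and Interactions sets the order on the day. After consent and the hearing questionnaire in pre-operative holding, "The patient's record in the electronic study database will then be created and randomized to one of two groups". The neurologist then tests the awake patient in the assigned mask. The macroelectrode is placed and tested, and "when confirmed the neurosurgeon will secure the macroelectrode in place". Next: "At this point, the neurologist's testing portion is complete, and the neurologist exits the operating room while the neurosurgeon completes the implantation". The questionnaire is triggered by the end of the neurologist's interaction, not by completed implantation.

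Outcomes and Statistical Plan names the primary endpoint (dichotomised question 1 of the CG-CAHPS), 30 patients per group, and Fisher's exact test to "investigate a difference between the standard of care mask and the clear mask for all dichotomous outcomes". It names no analysis set and gives no rule for missing answers.

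**The concern.** The inclusion criterion turns on what the patient has chosen; the exclusion turns on what happened in surgery. Anyone approached before surgery has already elected placement, so the exclusion seems to do little at screening. Its separate effect would fall on patients who chose placement and did not receive it, some of whom can be identified only after randomisation.

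That would be exclusion on a post-randomisation event. It need not be independent of arm, because the Background section ties accurate patient answers to good electrode placement, and the mask is meant to improve communication. With no stated analysis set, a randomised patient with a valid question 1 answer might be kept or dropped after the data are seen. In a trial of 60 with no allowance for losses, one such decision could settle significance.

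**Working it through.** **1. The plan's own figure.** Inputs from Outcomes and Statistical Plan: 73% versus 99% positive, 30 per group, two-sided Fisher's exact test, alpha 5%, stated power 80%. Exact power is the sum, over all pairs (x, y) with Fisher p < 0.05, of Bin(x; 30, 0.73) × Bin(y; 30, 0.99).

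- 30 per arm: 78.1%
- 31 per arm: 80.5%
- 29 per arm: 75.5%

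The stated design reproduces to within two points.

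**2. When the criterion is applied.** The sequence, assembled from the sections above:

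| Step | Event |
|---|---|
| 1 | Screening against the criteria, then approach |
| 2 | Consent and baseline hearing questionnaire |
| 3 | Randomisation |
| 4 | Awake testing in the assigned mask |
| 5 | Macroelectrode placed, tested and secured |
| 6 | Neurologist leaves; question 1 is asked |
| 7 | Neurosurgeon completes the implantation |

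Two sections put the criteria at step 1. None applies a criterion at steps 4 to 7. The line also has an ordinary use before consent: patients are telephoned in the days before surgery and consented that morning, and one whose operation is cancelled in between still meets the inclusion wording but is not a candidate.

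**3. Who could be affected.** Suppose the line were nevertheless applied after randomisation.

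- Surgery stopped before the neurologist's interaction: no question 1 answer exists, so a rule analysing all randomised patients with an answer would not include the patient either.
- Surgery following the described course: the electrode is secured at step 5, before question 1 at step 6, so the exclusion does not bite.
- Surgery abandoned during or just after testing, with the patient still able to answer: the only group at issue. The documents give no frequency.

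**4. What one removal could do.** This is conditional on a removal being made. Two-sided Fisher p, covered versus clear; the tables are assumed illustrations.

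| Removal | Before | After |
|---|---|---|
| One clear-mask negative | 22/30 v 28/30, p = 0.080 | 22/30 v 28/29, p = 0.026 |
| One covered-mask negative | 22/30 v 28/30, p = 0.080 | 22/29 v 28/30, p = 0.080 |
| One negative from each arm | 22/30 v 28/30, p = 0.080 | 22/29 v 28/29, p = 0.052 |
| One covered-mask positive | 25/30 v 30/30, p = 0.052 | 24/29 v 30/30, p = 0.024 |

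Over all 30/30 tables with the clear mask at least as good as the covered mask:

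- Removing one clear-mask negative changes significance in 25 tables, with total probability 6.8% at 73% versus 99% (17.2% at an assumed 73% versus 95%).
- Removing one covered-mask positive also changes significance in 25 tables, with probability 9.8% at 73% versus 99%.
- Removing one covered-mask negative changes significance in none.

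Every change is from non-significant to significant. Both arms are sensitive, so no particular mask is singled out. At the planned 99%, the clear arm expects 30 × 0.01 = 0.3 negatives, and 0.99^30 = 74% of trials would have none to remove. None of these figures is the chance that a removal happens.

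**The case for a change.** The strongest case for acting is that the line fails on either reading: as a screening rule it is close to redundant, and as a post-randomisation rule it is harmful, so deleting it costs nothing. The verb describes an event rather than an intention, the questionnaire does not wait for completed implantation, and nothing in the statistical plan settles the matter. In so small a trial, a choice left open until the data are seen is worth closing.

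Much of this stands. The wording is loose, the analysis set is unstated, and one patient can move the p-value across 0.05. What does not stand is the step from loose wording to a planned exclusion, which means setting aside two sections that place the criteria before approach. Redundancy proves little, since the neighbouring exclusion for patients who do not consent is also an enrolment condition stated in the negative. The silence on analysis population and missing answers would remain if this line were deleted, so it is not a fault of the line.

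**Conclusion.** No change to the plan follows. Followed as written, the criteria are applied before randomisation, and an analyst comparing the randomised groups on question 1 would use every patient with an answer, by assigned mask. That gives the same result as a version without this exclusion, except where surgery is abandoned during or just after testing and the patient still answers. That case looks rare from the described sequence, but its rate is not given.

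The p-value shifts in either arm are real arithmetic, but they depend on a discretionary removal that no sentence orders. They show that a trial of this size is fragile to any single lost patient; they do not show bias from this line. Tidier wording and a stated analysis set would be good housekeeping, with no demonstrated gain in the result.

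The conclusion assumes that the screening sections mean what they say and that no randomised patient with an answer is dropped for want of placement. A report showing such a removal would reopen the point.

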## **Interventions and Interactions**

Patients who both elect to undergo DBS surgery and agree to participate in this study will have a record created in the study database. All patients scheduled for a DBS phase I surgery will be contacted via telephone in the days prior to their scheduled surgery to discuss the possibility of study participation. This will be done to give the patient time to consider study participation in order to avoid delays the morning of surgery. The morning of surgery the patient will be approached in pre-operative holding room to discuss participation in the study and if amenable sign consent for participation. This discussion will inform the patient that minor changes are being made in an attempt to improve the patient experience, but limited information regarding what steps exactly will be provided so as to reduce potential bias that might result from the patient knowing we are studying a new mask type. If the patient agrees to participation, a consent form will be signed and as a baseline will undergo the Hearing Handicap Inventory for the Elderly (HHIE-S) questionnaire before the operation (Appendix 1). The patient's record in the electronic study database will then be created and randomized to one of two groups. Group A will experience the neurologist wearing a clear mask, and group B will experience the neurologist wearing a standard covered mask. The patient and all other intra-operative personnel will wear a covered surgical mask.

Following standard surgical protocol, the DBS surgery will proceed with the patient awake. First, a stereotactic frame is securely attached to the patient's head and the patient is positioned appropriately. Local anesthetic is used for the neurosurgeon to obtain access through the scalp and skull. A microelectrode is then stereotactically placed using headframe coordinates. The neurosurgeon sets up the motor apparatus to allow the neurologist to advance the microelectrode to the appropriate deep brain target, operating the motor from a non-sterile station arranged next to the patient. The microelectrode will stimulate and record neuronal activity, during which time the neurologist will ask the patient questions to assess for changes in symptoms. These questions typically are of the following nature:

- Do you notice any tingling or pulling of the mouth or face?
- Do you see any flashes of light in your vision?
- Do you feel any tingling or heaviness of an arm or leg?
- Do you notice any metallic or strange taste?
- Can you draw a spiral on this piece of paper?
- Can you hold your arm out in front of you and keep it still?

During a routine DBS surgery, the neurologist is positioned in view of the patient while operating the electrode motor and asking the above questions. Microelectrode stimulation and recording will conclude

when the appropriate target has been reached; that is, when simulation achieves both symptom improvement without new neurologic symptoms. At that point, the microelectrode is withdrawn and the macroelectrode is placed. The macroelectrode is stimulated in the determined position to again confirm symptom improvement without new neurologic symptom or deficit, and when confirmed the neurosurgeon will secure the macroelectrode in place. At this point, the neurologist's testing portion is complete, and the neurologist exits the operating room while the neurosurgeon completes the implantation.

For patients who agree to study participation, the neurologist will wear the mask type assigned by the randomization group for the duration of involvement in the surgery. At the conclusion of the neurologist's interaction with the patient, the patient will be asked a series of questions (presented in Appendix 2, Data collection form) to evaluate the communication experience. This step will be performed by another member of the study team (not the participating neurologist) who will read from the questionnaire and record the patient's responses using the Likert scale (defined in Appendix 2). During questioning, the neurologist will step out of the operating room to reduce potential bias from the patients answering subjective questions in front of the neurologist.

At the conclusion of the questionnaire, the patient will undergo a short debriefing regarding the aims of the study, specifically the revelation that the purpose of the study is to evaluate the use of a clear surgical mask on the patient's experience, as assessed by the questionnaire.

At the conclusion of the neurologist's assessment, as is typical, the patient will be placed under sedation for the completion of the DBS implantation. In the event a patient is having bilateral DBS implantation in one operation, only the first DBS implantation will be included in the study. For these patients, the procedure will be carried out as stated above, but following the first DBS implantation the neurologist will continue to interact with the patient for the second DBS implantation. The second implantation will not be included in the study data collection.

A retrospective chart review will be conducted for the 30 day post-operative period to evaluate for surgery-related infection. Evaluating for rates of infection between mask groups will help to ensure there is no harm associated with use of a non-covered mask during the operation. The patients will not need to be contacted or otherwise actively participate in the study during this period; information will be obtained via medical record review only. For such a chart review, a waiver of consent will be completed in the IRB application. Such a waiver is necessary in order to answer the study question regarding mask safety and surgery-related infection, as it would be difficult to retrospectively re-consent every patient already enrolled in this nearly-complete study.

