### **Informed Consent**

Written informed consent will be obtained prior to data collection or randomization. The risk of harm or discomfort is expected to be negligible, as the intraoperative questionnaire is short and not expected to extend the length of surgery more than 15 minutes. In addition, the clear mask has been approved for use in the operating room by the Food and Drug Administration and is not expected to increase the risk of infection compared to the standard covered mask. The rights and welfare of study participants will be protected by using measures to maintain the confidentiality of study information. Study results will be presented or published in lieu of providing individual subjects additional information regarding the study.

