### **Reporting of Unanticipated Problems, Adverse Events or Deviations**

Any unanticipated problems, serious and unexpected adverse events, deviations, or protocol changes will be promptly reported by the principal investigator or designated member of the research team to the IRB and sponsor or appropriate government agency if appropriate.

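### The late-added infection comparison is given a no-harm purpose that about 30 patients per arm cannot serve, and the plan sets no estimate or limit for it (minor)

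*Combined protocol and SAP*

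**What the plan says.** The Objective concerns the patient's "experience during awake brain surgery when the communicating neurologist wears a clear face mask" compared with a standard mask. Infection is not mentioned there.

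Interventions and Interactions adds a retrospective chart review for surgery-related infection over 30 days after the operation. Its purpose is given as: "Evaluating for rates of infection between mask groups will help to ensure there is no harm associated with use of a non-covered mask". The consent waiver is justified in similar terms: "Such a waiver is necessary in order to answer the study question regarding mask safety and surgery-related infection". The same sentence refers to "every patient already enrolled in this nearly-complete study", so the review came late.

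Outcomes and Statistical Plan sizes the trial on CG-CAHPS question 1 alone: "Thirty subjects per group will be needed to achieve 80% power to detect a difference of 26% or more between proportions". The secondary outcomes are the remaining questionnaire items and the free text. Infection is not listed, and no infection rate, interval or margin is given. One sentence could be read to reach it: "Fisher's Exact Test will be used to investigate a difference between the standard of care mask and the clear mask for all dichotomous outcomes", with p < 0.05 as the criterion.

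Informed Consent says separately that the FDA-approved clear mask "is not expected to increase the risk of infection compared to the standard covered mask".

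**The concern.** A comparison meant to help exclude harm needs some statement of how large a harm it could exclude. Here there is a purpose and a study question, but no estimate and no limit on interpretation. If the general Fisher rule applies, its only stated output is significant or not significant, and a small number of infections will almost always be not significant. That outcome would fit the stated purpose while sizeable increases remained compatible with the data.

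What is at stake is the safety sentence in the eventual report, and what the IRB is told the chart review can deliver. The primary analysis is not affected.

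**Working it through.** **Inputs.** From Outcomes and Statistical Plan: 30 per group, 60 in total, 73% versus 99%, two-sided Fisher's exact test at 5%, 80% power. From Interventions and Interactions: a 30-day chart review compared between mask groups. The documents give no infection rate, and none is assumed below. The number of charts is not stated, so 30 per arm is taken from the enrolment goal.

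**1. The plan's own figure.** Exact power is the sum of Bin(x; 30, 0.73) × Bin(y; 30, 0.99) over all tables with Fisher p ≤ 0.05. This gives 78.1% at 30 per group and 80.5% at 31. The stated 80% at 30 per group is reproduced to within 2 points. The size therefore answers a question about a 26-point difference in a questionnaire response. Infection plays no part in it.

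**2. Most an event-free result could exclude.** The Newcombe upper limit for clear minus covered is

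(p1 − p2) + √[(u1 − p1)² + (p2 − l2)²],

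where u1 is the Wilson upper limit in the clear arm and l2 the Wilson lower limit in the covered arm. With no events in either arm, p1 = p2 = l2 = 0, and the limit reduces to u1 = z²/(n + z²).

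- Two-sided 95% (z = 1.960): 3.841/(30 + 3.841) = 11.35 points.
- One-sided 95% (z = 1.645): 2.706/(30 + 2.706) = 8.27 points.

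**3. Does the method matter?** Upper limits at 0/30 versus 0/30:

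| Method | Limit (points) |
|---|---|
| Newcombe, one-sided 95% | 8.3 |
| Agresti-Caffo, two-sided 95% | 8.5 |
| Exact, clear arm alone, one-sided: 1 − 0.05^(1/30) | 9.5 |
| Newcombe, two-sided 95% | 11.4 |
| Miettinen-Nurminen, two-sided 95% | 11.5 |
| Exact, clear arm alone, two-sided: 1 − 0.025^(1/30) | 11.6 |

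The range is about 8 to 12 points.

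**4. Other sparse results** (two-sided 95% Newcombe upper limit, clear versus covered, 30 per arm): 0 v 1 gives 8.3 points, 1 v 1 gives 13.6 and 1 v 0 gives 16.7. If only 25 charts per arm were available, 0 v 0 would give 3.841/28.841 = 13.3.

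**5. Size at which zero events would exclude less.** Solving z²/(n + z²) ≤ d gives n ≥ z²(1/d − 1). For d = 5 points, 3.8415 × 19 = 72.99, so 73 per arm. For d = 2 points, 3.8415 × 49 = 188.2, so 189 per arm.

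**6. If the Fisher sentence covers infection.** At 30 per arm, 5 v 0 gives p = 2 × C(30,5)/C(60,5) = 2 × 142,506/5,461,512 = 0.052. For 6 v 0, p = 2 × 593,775/50,063,860 = 0.024. Against no infections in the covered arm, six would be needed in the clear arm for significance. At 5 v 0 the two-sided Newcombe interval is +2.0 to +33.6 points, so test and interval would give different readings of the same table.

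**The case against.** The strongest reply is that nothing in the plan draws a wrong inference. The wording speaks of helping to ensure, which describes a contribution and not a demonstration. Small, unpowered safety look-backs are normal, and this one could show a gross excess. Infection is plainly subordinate: the objective, hypothesis, primary endpoint and sample size all concern patient experience. Only the neurologist's mask changes, and the neurologist works from a non-sterile station. The expectation of no added risk rests on the mask's FDA approval, not on this trial.

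Most of this stands, and it is why the point is minor. A reader might infer that the investigators intend to declare the clear mask safe on a non-significant test or a low count. The documents do not say so. Nor do they support the view that the trial should have been sized for infection, since that was never its objective.

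Two things remain. The waiver sentence is firmer than the no-harm sentence: it speaks of answering a safety question, which about 30 charts per arm cannot do. And the only analysis rule available is a difference test, whose non-significant result says nothing about how large an increase is excluded.

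It is also fair to say that the two-sided 11.4 is near the top of the range and that the worry is one-directional. The one-sided 8.3 is therefore given beside it, and the conclusion is the same with either. Power for infection would require an assumed infection rate, so no such figure is used.

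**Conclusion.** The concern holds as a minor one. The plan gives the infection comparison a no-harm purpose and calls it a study question, but provides no estimate and no limit on what may be concluded. At about 30 per arm, an event-free result still leaves an increase of about 8 to 12 points open, so the review can flag a gross excess but cannot support no harm.

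This rests on 30 analysable charts per arm and on conventional 95% limits. It needs no assumed infection rate. It does not imply that the clear mask raises infection risk, that a misreading is planned, or that the look-back should be abandoned.

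**What to change.** **Interventions and Interactions.** Replace the no-harm sentence with wording such as: *Surgery-related infection within 30 days will be described by mask group; the study is not sized to rule out an increase with the clear mask.* Bring the waiver sentence into line, so that the stated reason is to describe infection by mask group and not to settle a safety question.

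**Outcomes and Statistical Plan.** Add: *Late-added descriptive safety outcome: surgery-related infection within 30 days, reported as counts per arm with a two-sided 95% Newcombe interval for clear minus covered, by assigned mask, and by mask used where that differs. No significance test will be applied to this outcome. Zero or few events will not be read as no harm.* Appendix 2 already records both the assignment and the mask used. Leaving out the test removes the doubt over whether the general Fisher sentence applies, and avoids the conflicting readings at 5 v 0.

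**Cost.** Two sentences change and one short paragraph is added. There is no effect on the primary endpoint, sample size or conduct. The price is a weaker safety statement and an amendment, since "protocol changes will be promptly reported by the principal investigator or designated member of the research team to the IRB"; the IRB would also see a changed reason for the waiver.
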